#### Figure 1: Study Design Schema

a: Titration details are outlined in [Appendix A](#).

b: A subgroup of subjects (~12), who have been on Synthroid for at least 3 months prior to Screening and who have maintained adequate trough T4 (free and total) levels in the Maintenance Period will participate in a PK substudy. During Week 4 of the Maintenance Period, subjects will be housed in the CRU for 9 days and 8 nights to undergo PK sample collections at specified timepoints as outlined in [Table 5](#).

## 7.2. Number of Subjects

A total of up to approximately 44 subjects who meet all the inclusion criteria and none of the exclusion criteria will be enrolled into the study. Approximately 12 subjects will be enrolled in the PK substudy.

### 7.2.1. Subject Replacement

Subjects who withdraw from the study for any reason will not be replaced.

## 7.3. Treatment Assignment

All subjects receive open-label XP-8121 at a starting dose corresponding to 50% of the target XP-8121 dose (4x the daily oral levothyroxine dose, rounded up to the nearest 50  $\mu$ g).

## 7.4. Dose Titration and Adjustment Criteria

### 7.4.1. Target XP-8121 Dose Definition and Calculation

Predicted geometric mean AUC at steady state for XP-8121 1200  $\mu$ g was similar to the predicted geometric mean AUC at steady state for Synthroid 300  $\mu$ g. Based on PK modeling, an XP-8121 SC weekly dose of 4 times the daily oral levothyroxine dose is estimated to provide similar exposure (AUC). Thus, the target weekly dose of XP-8121 SC (in  $\mu$ g) is calculated as the current daily oral levothyroxine dose (in  $\mu$ g) multiplied by 4 rounded up to the nearest 50  $\mu$ g.

### 7.4.2. Titration Period

The XP-8121 SC initiation dose will correspond to 50% of the target weekly dose of XP-8121 SC (in  $\mu$ g). During the Titration Period, XP-8121 will be titrated at a rate intended to mitigate potential adverse effects of thyroid hormone excess, while avoiding prolonged under-replacement. The response to titration will be carefully monitored to avoid these effects.

During the Titration Period, XP-8121 will be titrated based on individual response to therapy (using blood fT4 trough concentration as a fast-response marker) at intervals no more frequent than every other week and in dosage increments corresponding to 25% of the target dose, up to a maximum of 125% of the target dose or 1500 µg (whichever is lower).

Operationally, each week subjects will return to the CRU for dosing and to have trough fT4 concentrations measured. Based on the fT4 concentration, the Titration Period will proceed as follows:

- If fT4 concentration is below or within normal range (study reference range: 0.78 to 1.42 ng/dL), and no signs/symptoms of thyroid hormones excess are present, the dose of XP-8121 SC will be increased by 25% of the target dose (eg, if fT4 concentration levels drawn at Week 2 of Titration Period are confirmed to be within the normal range at Week 3 of Titration Period, XP-8121 will be increased to 75% of the target weekly XP-8121 SC dose). If a drug-related AE is reported or if overdosage is a concern, the Investigator should consult with the Medical Monitor before up-titrating.
- If fT4 is in the normal range with presence of signs/symptoms of thyroid excess, then XP-8121 titration will occur at the discretion of the Investigator and in discussion with the Medical Monitor.
  - Signs/symptoms of thyroid excess have differing dynamics (ie, start and worsen at varying time and rates) and are non-specific when assessed individually. Therefore, clinical judgment is needed to interpret them in the scenario of acute response to changes in the replacement levothyroxine dose using XP-8121. Investigators should determine whether solicited symptom(s) or observed sign(s) warrant a presumptive determination of thyroid excess (or intolerance of replacement therapy). Such determination should be made conservatively, considering the potential impact of the signs/symptoms on the subject well-being during the subsequent Maintenance Period (See [Appendix B](#) for a list of positive signs/symptoms of thyroid excess).
- If fT4 concentration exceeds the upper limit of normal (regardless of signs/symptoms of thyroid hormones excess), then XP-8121 titration will end, and the XP-8121 dosage will be lowered and held at the highest previously tolerated dose for the remainder of the study.

Once subjects have completed the Titration Period, they will continue at the same dose of XP-8121 in the Maintenance Period for 4 weeks (see [Appendix A](#) for details on titration algorithm).

#### 7.4.3. Maintenance Period

Subjects will remain on the dose of XP-8121 used at the end of the Titration Period.

If, during Maintenance Period, biochemical hyperthyroidism is present, as evidenced by elevated trough fT4 and/or low TSH, the Investigator may reduce the weekly dose of XP-8121 SC by one dose level (ie, 25% of the target dose) and maintain the lowered dose throughout the remainder of the study as tolerated. If multiple signs/symptoms of thyroid excess are present without definitive biochemical evidence of hyperthyroidism, the Investigator should confer with the Medical Monitor. If the Investigator and Medical Monitor agree to a XP-8121 dose reduction, the dose should be reduced by one dose level and held at the lowered dose for the remainder of the study, as tolerated.

## 8. SELECTION AND WITHDRAWAL OF SUBJECTS

### 8.1. Subject Inclusion Criteria

To be eligible, a subject must meet all the following inclusion criteria:

1. Provide written informed consent.
2. Male or female between the ages of 18 and 65 years (inclusive) at Screening, with chronic hypothyroidism and on a stable dose of oral levothyroxine (Synthroid or an FDA-approved generic equivalent to Synthroid) or, if in the PK substudy, Synthroid only for at least 3 months.
3. TSH within the normal range at Screening (study reference range: 0.47 to 4.68 µIU/mL) and at least 3 months prior to Screening (documented by local laboratory).
4. Free T4 within the normal range at Screening (study reference range: 0.78 to 1.42 ng/dL).
5. Women of childbearing potential (WOCBP) must have a negative urine pregnancy test at Screening and agree to use medically accepted contraception (except for contraceptives containing estrogen for PK substudy subjects only), or abstinence throughout the study.
6. Body Mass Index (BMI) 18 to 40 kg/m^2 at Screening.
7. Average triplicate blood pressure (BP) reading for systolic BP >90 mmHg and <150 mmHg and diastolic BP >40 mmHg and <100 mmHg at Screening.
8. Average triplicate resting heart rate/pulse >40 beats per minute (bpm) or <100 bpm at Screening.
9. Agrees to return to the CRU for all study visits, and if a part of the substudy PK group, remain at the CRU to comply with all required study procedures.

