Diagnosis and main entry criteria:	
Inclusion Criteria
 
To be eligible, a subject must meet all the following inclusion criteria:
 
 
1. Provide written informed consent.
 
2. Male or female between the ages of 18 and 65 years (inclusive) at Screening, with chronic hypothyroidism and on a stable dose of oral levothyroxine (Synthroid or an FDA-approved generic equivalent to Synthroid) or, if in the PK substudy, Synthroid only for at least 3 months.
 
3. TSH within the normal range at Screening (study reference range: 0.47 to 4.68 <math>\mu</math>IU/mL) and at least 3 months prior to Screening (documented by local laboratory).
 
4. Free T4 within the normal range at Screening (study reference range: 0.78 to 1.42 ng/dL).
 
5. Women of childbearing potential (WOCBP) must have a negative urine pregnancy test at Screening and agree to use medically accepted contraception (except for contraceptives containing estrogen for PK substudy subjects only), or abstinence throughout the study.
 
6. Body mass index (BMI) 18 to 40 <math>\text{kg}/\text{m}^2</math> at Screening.
 
7. Average triplicate blood pressure (BP) reading for systolic BP <math>>90</math> mmHg and <math><150</math> mmHg and diastolic BP <math>>40</math> mmHg and <math><100</math> mmHg at Screening.
 
8. Average triplicate resting heart rate/pulse <math>>40</math> bpm or <math><100</math> bpm at Screening.
 
9. Agrees to return to the CRU for all study visits, and if a part of the substudy PK group, remain at the CRU to comply with all required study procedures.
 
 
Exclusion Criteria
 
To be eligible a subject must not meet any of the following exclusion criteria:
 
 
1. History of hypersensitivity to levothyroxine (any formulation).
 
2. Current dose of oral levothyroxine based on body weight <math>>2</math> <math>\mu\text{g}/\text{kg}/\text{day}</math>.
 
3. Current levothyroxine total daily dose either <math><50</math> <math>\mu\text{g}</math> or <math>>375</math> <math>\mu\text{g}</math>.
 
4. Current use of combined thyroid treatment (i.e., Synthroid plus liothyronine or Synthroid plus Armour Thyroid) and/or any other levothyroxine aside from those used in the study.
 
5. Has renal insufficiency (serum creatinine <math>>3.0</math> mg/dL) or end-stage renal disease requiring renal replacement therapy.
 
6. Has any diagnosed hepatic disease affecting liver functionality or serum ALT or AST <math>>3</math> times the upper limit of normal (ULN).
 
7. Has hepatic synthetic insufficiency (eg, serum albumin <math><3.0</math> g/dL).
 
8. Has hematocrit of <math><33.5\%</math> for females and <math><38.7\%</math> for males.
 
9. Has hemoglobin of <math><10.8</math> g/dL for females and <math><12.8</math> g/dL for males.
 
10. Has clinically significant ECG abnormalities at Screening.
 
11. Has congestive heart failure, New York Heart Association (NYHA) Class III or IV.
 
12. Has history of myocardial infarction, unstable angina, or revascularization within 6-months prior to Screening.
 
13. Has history of a cerebrovascular accident within 6 months prior to Screening with major neurological deficits.
 
14. Has active malignancy within 5 years prior to Screening (except: basal cell or squamous cell skin cancers).
 
15. Has had major surgical operation within 60 days prior to Screening or planned surgical operation during the study.
 
16. Has a current bleeding disorder or platelet count <math><50 \times 10^9/\text{L}</math>.
 
17. Has donated blood or plasma within 7 days prior to Screening Visit or plans to donate within 7 days prior to Screening or during the study.
 
18. Use of supplements containing biotin within 7 days prior to Screening and during the study.
 

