### 8.2. Subject Exclusion Criteria

To be eligible a subject must not meet any of the following exclusion criteria:

1. History of hypersensitivity to levothyroxine (any formulation).
2. Current dose of oral levothyroxine, based on body weight >2 µg/kg/day.
3. Current levothyroxine total daily dose either <50 µg or >375 µg.
4. Current use of combined thyroid treatment (ie, Synthroid plus liothyronine or Synthroid plus Armour Thyroid) and/or any other levothyroxine aside from those used in the study.
5. Has renal insufficiency (serum creatinine >3.0 mg/dL) or end-stage renal disease requiring renal replacement therapy.
6. Has any diagnosed hepatic disease affecting liver functionality or serum ALT or AST >3 times the upper limit of normal (ULN)
7. Has hepatic synthetic insufficiency (eg, serum albumin <3.0 g/dL).
8. Has hematocrit of <33.5% for females and <38.7% for males.
9. Has hemoglobin of <10.8 g/dL for females and <12.8 g/dL for males.
10. Has clinically significant ECG abnormalities at Screening.
11. Has congestive heart failure, New York Heart Association (NYHA) Class III or IV.
12. Has history of myocardial infarction, unstable angina, or revascularization within 6 months prior to Screening.
13. Has history of a cerebrovascular accident within 6 months prior to Screening with major neurological deficits.
14. Has active malignancy within 5 years prior to Screening (except: basal cell or squamous cell skin cancers).

15. Has had major surgical operation within 60 days prior to Screening or planned surgical operation during the study.
16. Has a current bleeding disorder or platelet count  $<50 \times 10^9/L$ .
17. Has donated blood or plasma within 7 days prior to Screening Visit or plans to donate within 7 days prior to Screening or during the study.
18. Use of supplements containing biotin within 7 days prior to Screening and during the study.
19. Participated in a clinical study within 30 days or 5 half-lives of the study drug prior to Screening.
20. Current use or history of using anticoagulants 14 days prior to Screening. (Use of aspirin greater than 325 mg/day is excluded).
21. Hemoglobin A1C (HbA1c)  $>8\%$  at Screening.
22. History of active substance or alcohol abuse within the 12 months prior to Screening. Abuse of alcohol defined as an average weekly intake of  $>21$  units (1 unit is equivalent to a half pint of beer, 1 serving of hard liquor, or 1 glass of wine).

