### 12.8.4. Vital Sign Measurements

Vital signs (systolic and diastolic BP, heart rate/pulse, respiratory rate, oral temperature) will be measured as described in the Schedule of Assessments ([Table 2](#)). Three readings of BP and heart rate/pulse should be taken at intervals of 1 to 2 minutes. The three readings of each will be recorded on the eCRF and assessed to determine eligibility for inclusion into the study and throughout the study (Section [8.1](#)).

Subjects should be resting for at least 10 minutes in a supine position prior to measurement of BP and heart rate/pulse. See [Table 3](#) for timing window allowances with respect to measurement collection. Where possible, assessments should be conducted in order of least invasive to most invasive (See Section [11.5](#) for details).

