**Table 9: Signs/Symptoms of Indicative of Hyperthyroidism**

Heat intolerance
Hyperkinesis
Atrial fibrillation
Excessive sweating
Increased Appetite
Decreased Weight
Casual heart rate/pulse >90 bpm
Palpitations
Tiredness
Nervousness
Hot hands
Shortness of breath
Moist hands
Tremor
Increased frequency of bowel movements
Urinary frequency and nocturia

[figure not shown]

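### Inclusion criterion 8 joins its two heart-rate limits with *or*, so every heart rate satisfies it and the criterion screens nobody out

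*Protocol*

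**What the plan says.** Protocol Section 8.1 requires a subject to meet every inclusion criterion. Criterion 8 is "Average triplicate resting heart rate/pulse >40 beats per minute (bpm) or <100 bpm at Screening". The synopsis repeats the connector: "bpm or <100 bpm at Screening".

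The criterion directly above it, criterion 7, sets blood-pressure limits. Its diastolic part uses the same two numbers in different units, joined the other way: "diastolic BP >40 mmHg and <100 mmHg at Screening".

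Section 12.8.4 has blood pressure and heart rate/pulse each read three times. It says the readings are "recorded on the eCRF and assessed to determine eligibility for inclusion into the study and throughout the study", with a reference back to Section 8.1.

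The only other heart-rate figure in the protocol is in Appendix B, Table 9: "Casual heart rate/pulse >90 bpm". It is listed there as a possible sign of hyperthyroidism, not as an entry limit.

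**The concern.** An inclusion criterion with a lower and an upper number is normally a range. With *or* between the numbers, a subject needs to satisfy only one side, and every possible heart rate satisfies at least one. The criterion then has no effect, although Section 12.8.4 relies on it as part of the eligibility assessment.

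What is at stake is eligibility and safety documentation, not inference. Under the current text, enrolling a subject with an average rate at or below 40 bpm, or at or above 100 bpm, is not a deviation from criterion 8. A monitor or auditor would have no numeric rule to cite. Heart rate is a relevant safety measure here: Section 12.3 requires clinically significant changes in it to be reported as adverse events, and SAP Section 6.9.5 analyses its change from baseline.

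**Working it through.** The plan gives no figure to reproduce. The check is one of logic, illustrated on a grid.

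**Inputs.** The limits >40 and <100 bpm joined by *or* (Section 8.1, criterion 8, and synopsis); the limits >40 and <100 mmHg joined by *and* (criterion 7, diastolic); the rule that all inclusion criteria must be met (Section 8.1).

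**Step 1: the criterion as written.** Let x be the average resting rate.
- If x ≤ 40, then x < 100, so the second condition holds.
- If x ≥ 100, then x > 40, so the first condition holds.
- If 40 < x < 100, both hold.

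The union of {x > 40} and {x < 100} is therefore every number, and nothing is excluded.

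**Step 2: the same numbers joined with *and*.** The intersection is 40 < x < 100. Rates at or below 40 and at or above 100 fail.

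**Step 3: illustration.** Whole-number rates from 20 to 200 bpm give 200 − 20 + 1 = 181 values.

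| Connector | Pass | Reject |
|---|---|---|
| *or* (as written) | 181 | 0 |
| *and* | 99 − 41 + 1 = 59 | 21 (20 to 40) + 101 (100 to 200) = 122 |

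A finer grid, 0 to 300 bpm in steps of 0.1 (3001 values), gives the same answer: *or* passes 3001, while *and* passes 599 (40.1 to 99.9) and rejects 2402. Of the spot values 30, 40, 70, 100 and 130 bpm, all five pass with *or* and only 70 passes with *and*.

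**Step 4: the other paired limits.** Sections 8.1 and 8.2 contain eight two-sided numeric limits.

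| Limit | Can it exclude a value? |
|---|---|
| Age 18 to 65 years | Yes |
| TSH 0.47 to 4.68 µIU/mL | Yes |
| Free T4 0.78 to 1.42 ng/dL | Yes |
| BMI 18 to 40 kg/m² | Yes |
| Systolic BP >90 and <150 mmHg | Yes |
| Diastolic BP >40 and <100 mmHg | Yes |
| Daily levothyroxine <50 or >375 µg (exclusion 3) | Yes |
| Heart rate >40 or <100 bpm | No |

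Exclusion 3 also uses *or*, but it joins the two outer regions of an exclusion, where *or* is the correct connector. Heart rate is the only one of the eight that does nothing.

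**Step 5: whether another rule supplies the limit.** None does. The nearest exclusions are number 10 ("Has clinically significant ECG abnormalities at Screening"), number 11 ("Has congestive heart failure, New York Heart Association (NYHA) Class III or IV") and number 12 ("Has history of myocardial infarction, unstable angina, or revascularization within 6 months prior to Screening"). Exclusion 25 covers other disease and investigator discretion. None of them states a heart rate.

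**The case against.** The strongest reply is that nobody will be misled. A low and a high number in one criterion, directly beneath a criterion that uses *and*, will be read as a range. The Version 3.0 revision summary, cited here only for intent, also shows that the average heart rate was meant to decide eligibility. Other screens remain as well: exclusions 10, 11, 12 and 25, ECG review with cardiologist referral (Section 12.8.5), normal TSH and free T4 at Screening, and Medical Monitor approval of each subject before titration (Section 14.1). All of this stands and keeps the consequence small. It does not make criterion 8 work, because none of those screens sets a heart-rate number and eligibility is enforced on the text.

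A second objection is that Section 12.8.4 does not strictly contradict Section 8.1. It sets no limit of its own, its eligibility step still works for blood pressure, and it needs no edit for this error once criterion 8 is corrected. That is fair. The inconsistency is that Section 12.8.4 sends the reader to a heart-rate test that cannot fail; the defect itself lies in criterion 8.

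A third is that the grid counts depend on the range chosen and do not measure subjects affected. That is also right. They illustrate the logic and are not an effect size.

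**Conclusion.** The point holds. As written in both Section 8.1 and the synopsis, criterion 8 excludes no heart rate, and no other entry rule supplies a numeric limit. The conclusion rests only on the wording and needs no assumption about data.

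It is minor. It is a one-word error in an operative entry rule, softened by judgment-based screens and by the likelihood that sites read it as a range. The documents give no heart-rate distribution, so the number of subjects affected cannot be estimated and none is claimed. Sample size, power and the dose-conversion analysis are unaffected.

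**What to change.** Replace *or* with *and* in criterion 8 in both the synopsis and Section 8.1, leaving the sponsor's two limits as they are, and have the sponsor confirm that this is the intended range. Then confirm that criterion 8 and Section 12.8.4 agree. One wording point can be settled at the same time: criterion 8 tests the average of the triplicate, whereas Section 12.8.4 speaks of the three readings being assessed.

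Check that the eligibility eCRF and the Enrollment Authorization Request Form (Section 14.1) carry the corrected wording; their text is not in the documents. If subjects have already been enrolled under the current wording, Section 12.8.4 puts their three readings on the eCRF, so anyone at or outside either limit can be identified without new data.

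The cost is one word in two places, plus the IRB/IEC re-approval that Section 16.1 requires for amendments. It can be carried in the next amendment.

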### 8.2. Subject Exclusion Criteria

To be eligible a subject must not meet any of the following exclusion criteria:

1. History of hypersensitivity to levothyroxine (any formulation).
2. Current dose of oral levothyroxine, based on body weight >2 µg/kg/day.
3. Current levothyroxine total daily dose either <50 µg or >375 µg.
4. Current use of combined thyroid treatment (ie, Synthroid plus liothyronine or Synthroid plus Armour Thyroid) and/or any other levothyroxine aside from those used in the study.
5. Has renal insufficiency (serum creatinine >3.0 mg/dL) or end-stage renal disease requiring renal replacement therapy.
6. Has any diagnosed hepatic disease affecting liver functionality or serum ALT or AST >3 times the upper limit of normal (ULN)
7. Has hepatic synthetic insufficiency (eg, serum albumin <3.0 g/dL).
8. Has hematocrit of <33.5% for females and <38.7% for males.
9. Has hemoglobin of <10.8 g/dL for females and <12.8 g/dL for males.
10. Has clinically significant ECG abnormalities at Screening.
11. Has congestive heart failure, New York Heart Association (NYHA) Class III or IV.
12. Has history of myocardial infarction, unstable angina, or revascularization within 6 months prior to Screening.
13. Has history of a cerebrovascular accident within 6 months prior to Screening with major neurological deficits.
14. Has active malignancy within 5 years prior to Screening (except: basal cell or squamous cell skin cancers).

15. Has had major surgical operation within 60 days prior to Screening or planned surgical operation during the study.
16. Has a current bleeding disorder or platelet count  $<50 \times 10^9/L$ .
17. Has donated blood or plasma within 7 days prior to Screening Visit or plans to donate within 7 days prior to Screening or during the study.
18. Use of supplements containing biotin within 7 days prior to Screening and during the study.
19. Participated in a clinical study within 30 days or 5 half-lives of the study drug prior to Screening.
20. Current use or history of using anticoagulants 14 days prior to Screening. (Use of aspirin greater than 325 mg/day is excluded).
21. Hemoglobin A1C (HbA1c)  $>8\%$  at Screening.
22. History of active substance or alcohol abuse within the 12 months prior to Screening. Abuse of alcohol defined as an average weekly intake of  $>21$  units (1 unit is equivalent to a half pint of beer, 1 serving of hard liquor, or 1 glass of wine).
23. Positive urine drug screen (except: if the results are positive for a benzodiazepine that is being taken as a prescribed concomitant medication, as defined and documented in accordance with the protocol).
24. Positive blood screen for human immunodeficiency virus (HIV), hepatitis B surface antigen (HBsAg), or hepatitis C antibodies at Screening.
25. Has a history of clinically significant or uncontrolled gastrointestinal, neurologic, hematologic, endocrine (with the exception of hypothyroidism), oncologic, pulmonary, immunologic, psychiatric, or cardiovascular disease, or any other condition which could jeopardize the safety of the subject or impact the validity of the study results,  
**OR**  
Any reason the Investigator or designee deems exclusionary.
26. **For PK substudy only:** Use of any estrogen-containing compound within 14 days prior to Day 1 of the Titration Period and throughout the study.
27. **For PK substudy only:** On medical examination (at Screening) by the Investigator or designee, has inadequate or difficult venous access that may jeopardize the quality or timing of the PK samples.

